## **Site Operations Manual (SOM)**

A Site Operations Manual (SOM) accompanies this protocol, providing the operational details for study conduct. Note: The SOM will not be part of the Clinical Study Report.

### **Notification of serious adverse events**

**Dear Investigator,**

You must report a serious adverse event (SAE) or serious adverse device effect (SADE) (initial or follow-up) to Novartis as summarized below. Refer to [Section 9.3](#) of the protocol for SAE and SADE criteria and additional requirements. See also page 2 of the Site Operations Manual for further details on the method of reporting a SAE and SADE.

- Complete SAE and SADE reports
- Submit SAE or SADE report to Chief Medical Office & Patient Safety (CMO&PS) **within 24 hours after awareness of the SAE or SADE** Notify the Novartis Medical Lead
- The fax number(s) and email address(es) are located in the Site Operations Manual.

## List of abbreviations

$\gamma$ -GT	Gamma-glutamyl transferase
ACI	Autologous Chondrocyte Implantation
ADE	Adverse device effect
AE	adverse event
ALP	alkaline phosphatase
ALT	alanine aminotransferase
ANCOVA	analysis of covariance
ANGPTL	angiopoietin-like protein
AST	aspartate aminotransferase
B	Blinded
BMI	Body Mass Index
BP	Blood Pressure
BUN	blood urea nitrogen
CFR	Code of Federal Regulations
CK	creatinine kinase
CMO&PS	Chief Medical Office & Patient Safety
COAs	Clinical Outcome Assessments
CPPD	Calcium Pyrophosphate Deposition Disease
CRF	Case Report/Record Form (paper or electronic)
CRO	Contract Research Organization
CTC	Common Toxicity Criteria
CTRД	Clinical Trial Results Database
CV	coefficient of variation
DMC	Data Monitoring Committee
DNA	Deoxyribonucleic Acid
EC	Ethics committee
ECG	Electrocardiogram
EDC	Electronic Data Capture
ELISA	Enzyme-linked immunosorbent assay
EOS	End of Study
FDA	Food and Drug Administration

---

FIH	First in Human
GAG	Glycosaminoglycan
GCP	Good Clinical Practice
h	Hour
HBV	Hepatitis B
HCV	Hepatitis C
HDL	High-Density Lipoproteins
HIV	human immunodeficiency virus
i.a.	intra articular
ICH	International Conference on Harmonization of Technical Requirements for Registration of Pharmaceuticals for Human Use
IEC	Independent Ethics Committee
IG	Immunogenicity
IRB	Institutional Review Board
IRT	Interactive Response Technology
IUD/IUS	Intrauterine Device or System

**Corporate Confidential Information**

LDH	lactate dehydrogenase
LDL	Low-density Lipoprotein
LFT	Liver function test
LLN	lower limit of normal
LLQ	lower limit of quantification
MABEL	minimum anticipated biological effect level
MedDRA	Medical dictionary for regulatory activities
mg	milligram(s)
mL	milliliter(s)
[name]
MOCART	Magnetic resonance Observation of Cartilage Repair Tissue
MRI	Magnetic Resonance Imaging
NCDS	Novartis Clinical Data Standards
NSAID	Non steroidal anti-inflammatory drugs
NIRT	Novartis Interactive Response Technology

OA	Osteoarthritis
o.d.	once a day
PCR	Polymerase Chain Reaction
PD	pharmacodynamic(s)
PK	pharmacokinetic(s)
PoC	Proof of Concept
PRO	Patient-Reported Outcomes
RBC	red blood cell(s)
RDC	Remote Data Capture
REB	Research Ethics Board
RF	Radiofrequency
RNA	Ribonucleic Acid
s.c.	Subcutaneous
SAE	serious adverse event
SAD	single ascending dose
SADE	serious adverse device effect
SAR	Specific absorption rate
sCR	serum creatinine
SD	standard deviation
SOM	Site Operations Manual
SUSAR	Suspected Unexpected Serious Adverse Reactions
TBL	total bilirubin
TKR	Total Knee Replacement
ULN	upper limit of normal
ULQ	upper limit of quantification
USADE	unanticipated serious adverse device effect
WBC	white blood cell(s)
WHO	World Health Organization
7T MRI	7 Tesla MRI

## Pharmacokinetic definitions and symbols

Ae0-t	Amount of drug (or defined metabolite) excreted into the urine from time zero to time 't' where t is a defined time point after administration [mass units or % of dose]
AUC0-t	The area under the plasma (or serum or blood) concentration-time curve from time zero to time 't' where t is a defined time point after administration [mass x time / volume]
AUCinf	The area under the plasma (or serum or blood) concentration-time curve from time zero to infinity [mass x time / volume]
AUClast	The area under the plasma (or serum or blood) concentration-time curve from time zero to the time of the last quantifiable concentration [mass x time / volume]
AUCtau	The area under the plasma (or serum or blood) concentration-time curve from time zero to the end of the dosing interval tau [mass x time / volume]
AUCtau,ss	The area under the plasma (or serum or blood) concentration-time curve from time zero to the end of the dosing interval tau at steady state [mass x time / volume]
Cav,ss	The average steady state plasma (or serum or blood) concentration during multiple dosing
CL	The systemic (or total body) clearance from plasma (or serum or blood) following intravenous administration [volume / time]
CL/F	The apparent systemic (or total body) clearance from plasma (or serum or blood) following extravascular administration [volume / time]
CLr	The renal clearance from plasma (or serum or blood) [volume / time]
Cmax	The observed maximum plasma (or serum or blood) concentration following drug administration [mass / volume]
Cmax,ss	The observed maximum plasma (or serum or blood) concentration following drug administration at steady state [mass / volume]
Cmin,ss	The lowest plasma (or serum or blood) concentration observed during a dosing interval at steady state [mass / volume]
F	Bioavailability of a compound. Fabs is the absolute bioavailability, i.e. the fraction (or percentage) of the administered extravascular dose systemically available. Frel is the relative bioavailability, i.e. the bioavailability relative to a reference
MRT	Mean residence time determined as AUMCinf/AUCinf following intravenous administration [time]
Racc	The accumulation ratio
T1/2	The terminal elimination half-life [time]

T1/2,acc	The effective half-life based on drug accumulation at steady state [time]
Tmax	The time to reach the maximum concentration after drug administration [time]
Vss	The volume of distribution at steady state following intravenous administration [volume]
Vz	The volume of distribution during the terminal elimination phase following intravenous administration [volume]
Vz/F	The apparent volume of distribution during the terminal elimination phase following extravascular administration [volume]

## Glossary of terms

Assessment	A procedure used to generate data required by the study
Cohort	A specific group of subjects fulfilling certain criteria
Control drug	Any drug (an active drug or an inactive drug, such as a placebo) which is used as a comparator to the investigational drug being tested in the trial
Dosage	Dose of the study treatment given to the subject in a time unit (e.g. 100 mg once a day, 75 mg twice a day)
Enrollment	Point/time of subject entry into the study at which informed consent must be obtained (i.e. prior to starting any of the procedures described in the protocol)
Epoch	Interval of time in the planned conduct of a study. An epoch is associated with a purpose (e.g. screening, randomization, treatment, follow-up), which applies across all arms of a study.
Healthy volunteer	A person with no known significant health problems who volunteers to be a study participant
Investigational drug	The study drug whose properties are being tested in the study; this definition is consistent with US CFR 21 Section 312.3 and Directive 2001/20/EC and is synonymous with “investigational new drug” or “test substance”
Investigational treatment	All investigational drug(s) whose properties are being tested in the study as well as their associated treatment controls. This includes any placebos, any active controls, as well as approved drugs used outside of their indication/approved dosage or tested in a fixed combination. Investigational treatment generally does not include other treatments administered as concomitant background therapy required or allowed by the protocol when used within approved indication/dosage.
Medication number	A unique identifier on the label of each study drug package in studies that dispense study drug using an IRT system.
Medication pack number	A unique identifier on the label of each drug package in studies that dispense study treatment using an IRT system
Non-investigational medicinal Product (NIMP)	Products which are not the object of investigation (e.g. any background therapy administered to each of the clinical trial subjects, regardless of randomization group, rescue medication, active drug run-ins etc.)
Part	A single component of a study which contains different objectives or populations within that single study. Common parts within a study are: a single dose part and a multiple dose part, or a part in patients with established disease and in those with newly-diagnosed disease.
Patient	An individual with the condition of interest

Period	A minor subdivision of the study timeline; divides phases into smaller functional segments such as screening, baseline, titration, washout, etc.
Personal Data	Subject information collected by the Investigator that is transferred to Novartis for the purpose of the clinical trial. This data includes subject identifier information, study information and biological samples.
Premature subject withdrawal	Point/time when the subject exits from the study prior to the planned completion of all study drug administration and assessments; at this time all study drug administration is discontinued and no further assessments are planned.
Randomization number	A unique identifier assigned to each randomized subject, corresponding to a specific treatment arm assignment
Screen Failure	A subject who is screened but is not treated or randomized
Stage	A major subdivision of the study timeline; begins and ends with major study milestones such as enrollment, randomization, completion of treatment, etc.
Study completion	Point/time at which the subject came in for a final evaluation visit or when study drug was discontinued whichever is later.
Study drug discontinuation	Point/time when subject permanently stops taking study drug for any reason; may or may not also be the point/time of premature subject withdrawal.
Study drug/treatment	Any drug (or combination of drugs) administered to the subject as part of the required study procedures; includes investigational drug, active drug run-ins or background therapy.
Study treatment	Any drug administered to the study participants as part of the required study procedures; includes investigational drug (s), control(s) or non-investigational medicinal product(s)
Study treatment discontinuation	When the subject permanently stops taking study treatment prior to the defined study treatment completion date
Subject	A trial participant (can be a healthy volunteer or a patient)
Subject number	A unique number assigned to each subject upon signing the informed consent. This number is the definitive, unique identifier for the subject and should be used to identify the subject throughout the study for all data collected, sample labels, etc.
Treatment number	A unique identifier assigned in non-randomized studies to each dosed subject, corresponding to a specific treatment arm
Variable	A measured value or assessed response that is determined in specific assessments and used in data analysis to evaluate the drug being tested in the study

Withdrawal of study  
consent

Withdrawal of consent from the study occurs only when a subject does not want to participate in the study any longer, and does not allow any further collection of personal data

**Corporate Confidential Information**

## Protocol synopsis

Protocol number	CLNA043X2201
Title	A randomized, placebo-controlled, patient and investigator blinded, single dose, Proof of Concept study investigating the safety, tolerability and preliminary efficacy of intra-articular LNA043 in regenerating the articular cartilage of the knee at donor sites in patients undergoing autologous chondrocyte implantation.
Brief title	Study of safety and tolerability and preliminary efficacy of LNA043 in patients undergoing autologous chondrocyte implantation.
Sponsor and Clinical Trial Phase	Novartis Phase II
Intervention type	Biologic
Study type	Interventional
Purpose and rationale	The purpose of this Proof of Concept (PoC) study is to assess safety, tolerability and preliminary efficacy of intra articular (i.a.) LNA043 in regenerating the articular cartilage of the knee at the donor sites of the autologous chondrocyte implantation (ACI) procedure, with a hyaline tissue, significantly more often than with placebo. The highest single safe dose of LNA043 of the First in Human CLNA043X2101 study will be used.
Primary Objective(s)	
 
To assess the efficacy of a single LNA043 i.a. injection in regenerating hyaline cartilage tissue at the donor sites of patients undergoing autologous chondrocyte implantation (ACI)
 
To assess safety and tolerability of a single LNA043 i.a. injection in patients undergoing ACI
 

Secondary Objectives	
 
To assess extent and quality of the repair tissue at the donor site before surgery
 
To assess over a longer term the extent and quality of filling of the donor site
 
To evaluate local and systemic pharmacokinetics (PK) of LNA043 following a single i.a. administration
 
To assess the potential immunogenicity of LNA043
 

Study design	Randomized, placebo-controlled, patient and investigator blinded, parallel group, 2 cohorts, single dose, 6 month study
Population	Approximately 22 patients (18-50 years of age) undergoing autologous chondrocyte implantation to allow approximately 18 completers, divided as follow: approximately 12 completers in Cohort 1 and approximately 6 completers in Cohort 2. The two cohorts differ only by the dose administered: 20 mg LNA043 or matching placebo in Cohort 1, 40 mg LNA043 or matching placebo in Cohort 2
Key Inclusion criteria	
 
Written informed consent must be obtained before any assessment is performed
 
Patient is <math>\geq 18</math> and <math>\leq 50</math> years old at time of screening
 
Patient has a body mass index (BMI) <math><30 \text{ kg/m}^2</math> at screening
 
Patient has a localized articular cartilage defect of the knee and is scheduled for an ACI procedure
 

	

• Able to communicate well with the investigator, to understand and comply with the requirements of the study.

Key Exclusion criteria	

• Patient has radiologically apparent degenerative joint disease in the target knee as determined by Kellgren and Lawrence grade <math>\geq 2</math> based on X-ray evaluation performed within 6 months from screening

• Patient has unstable knee joint or insufficiently reconstructed ligaments, based on medical history and physical examination by the investigator.

• Patient scheduled for a concomitant articular surgical procedure (e.g., anterior cruciate ligament reconstruction) other than debridement or partial meniscectomy

• Patient has malalignment (valgus- or varus-deformity) in the target knee <math>\geq 5^\circ</math> based on X-ray evaluation performed within 6 months from screening.

• Patient has a known autoimmune disease, inflammatory arthropathy (including but not limited to rheumatoid arthritis, psoriatic arthritis, ankylosing spondylitis, CPPD, gout), active acute or chronic infection of the joint, recent Lyme disease to the knee, systemic cartilage disorder, or a known systemic connective tissue disease.

• Patient has had surgical treatment of the target knee using autologous osteochondral transplantation/mosaicplasty within 12 months prior to screening (Note: prior diagnostic arthroscopy with debridement and lavage, meniscal surgery, microfracture, anterior cruciate ligament reconstruction, and extra-articular surgery e.g., high-tibial osteotomy are acceptable).

• Patient is unable to undergo magnetic resonance imaging (MRI) or presents absolute contraindications to MRI (e.g., metallic implants, metallic foreign bodies, pacemaker, defibrillator).

• Patient taking medications prohibited by the protocol: corticosteroids by any route (except topical) from 4 weeks prior to screening; nonsteroidal anti-inflammatories or aspirin (greater than 100 mg per day) within 2 weeks prior to screening; paracetamol greater than 3000 mg per day within 2 weeks prior to screening; glucosamine or chondroitin sulfate within 2 weeks prior to screening; any local treatment i.a. into the knee within 3 months from screening.

• Women of child-bearing potential, defined as all women physiologically capable of becoming pregnant, unless they are using highly effective methods of contraception during dosing and for 15 days after stopping of investigational drug.

• Regular smokers (use of tobacco/nicotine products in the previous 3 months <math>> 5</math> cigarettes/day). Urine cotinine levels will be measured during screening for all subjects. Regular smokers will be defined as any subject who reports tobacco use of <math>> 5</math> cigarettes/day and/or who has a urine cotinine <math>\geq 500</math> ng/mL.

Study treatment	
Cohort 1:
 

○ A: single dose of 20 mg LNA043

○ B: single dose of matching placebo to 20 mg LNA043

 
Cohort 2:
 

○ C: single dose of 40 mg LNA043

○ D: single dose of matching placebo to 40 mg LNA043

Efficacy/PD assessments	

• Cartilage glycosaminoglycan (GAG) content and bi-layer collagen organization based on 7 Tesla MRI (7T MRI)

• International Cartilage Repair Society (ICRS) II histology scoring system

• Percentage (%) of donor site filling based on 7T MRI

Key safety assessments	

• Adverse event monitoring

• Physical examinations

• Monitoring of laboratory markers in blood and urine

Other assessments	

• Serum PK profile of LNA043 and /AngPTL3

• Corporate Confidential Information

• Presence and characterization of anti-LNA043 antibodies in serum

Data analysis	The primary efficacy variable, GAG content change and bi-layer collagen organization in the cartilage repair tissue at the donor sites based on 7T MRI at Week 4, and key secondary endpoints, will be analyzed using a mixed model repeated measures (MMRM) analysis of variance model, including all timepoints, to compare treatment groups.
Key words	ACI, cartilage regeneration, 7T MRI

## 1 Introduction

### 1.1 Background

When articular cartilage damage occurs, there is no approved treatment to regenerate a durable hyaline cartilaginous tissue, capable to withstand joint function and support an active life style. Current surgical procedures (e.g., microfractures) typically lead to fibrous, fibrocartilaginous and/or calcified repair tissue with limited biochemical and biomechanical properties. Clinical evidence has also shown that untreated focal defects to the articular cartilage may progress, leading to osteoarthritis (OA) and requiring joint replacement later in life, with poor outcomes for the patients and high costs for the community. Therefore, there is a high unmet medical need for more effective and efficient ways of repairing the articular cartilage, in order to intervene earlier, less invasively and stop the disease progression to OA.

Articular cartilage has limited healing potential. During cartilage damage, the number of cartilage resident mesenchymal stem cells (CR-MSCs) increases. CR-MSCs are capable of multi-lineage differentiation, including chondrogenesis, when exposed to an appropriate signaling environment in vitro. The LNA043 program arose from an effort to identify molecules able to target CR-MSCs to undergo differentiation into chondrocytes and facilitate hyaline articular cartilage repair by inducing the production of SOX9, type II collagen and aggrecan, but not inducing molecules involved in fibrosis or osteogenesis.

#### Corporate Confidential Information

LNA043 acts directly on CR-MSCs and articular chondrocytes through binding to  $\alpha 5\beta 1$  and  $\alpha V\beta 3$  integrins (RGD class) on the cell surface to transmit its anabolic repair effects on cartilage cells. These events promote the formation of articular cartilage extracellular matrix proteins in mature chondrocytes and in CR-MSCs while supporting re-growth of CR-MSCs.

The first-in-human single ascending dose (FIH SAD) study initially investigated doses up to 20 mg, and then a further dose escalation to 40 mg was performed. FIH SAD has been performed in primary OA patients who were scheduled for total knee replacement (TKR). LNA043 was administered 1 week prior to surgery and safety, tolerability, pharmacokinetics (PK), immunogenicity data were collected. In summary, (i) no significant drug-related Adverse Events (AE) and Serious Adverse Events (SAE) have been reported up to the highest evaluated single i.a. dose of 40 mg; (ii) LNA043 was rapidly eliminated from the synovial fluid of the knee and the plasma (LNA043 levels were below limit of quantification after 7 days in both samples) and (iii) no anti-drug antibodies (ADA) were detected. Consequently after evaluating the data from the FIH on the 40 mg dose, it has been decided to use it in the CLNA043X2201 study. From a risk-benefit perspective no changes are foreseen. Considering the FIH SAD study results, the 40 mg dose was not associated with any significant drug related AEs or SAEs while the demonstrated dose/response in the pre-clinical studies indicate potential incremental treatment benefit which might be associated with an higher dose of LNA043.

Considering the previous pre-clinical and clinical experience, a potentially favorable benefit/risk is anticipated for the patients included in the present study. Potential benefits include (i) better healing of the donor sites; (ii) improved integration of the ACI graft; (iii) reduction in size of the cartilage defect, possibly resulting in a better outcome of the ACI procedure.

The most relevant data for the present study are summarized in the sections below. For detailed information, please refer to the Investigator's Brochure.

**Corporate Confidential Information**

**Corporate Confidential Information**

**Corporate Confidential Information**

### **Corporate Confidential Information**

#### **1.4 Study purpose**

The purpose of this study is to assess safety, tolerability, pharmacokinetics and preliminary efficacy of a single intra-articular (i.a.) administration of LNA043 in regenerating the articular cartilage of the knee, in a standardized clinical scenario of acute cartilage defect. This study is aimed at establishing Proof of Concept (PoC) and characterizing the mechanism(s) of action of LNA043, in order to provide information on the potential for clinical application, with the ultimate goal of replacing current surgical procedures for cartilage repair. A First In Human (FIH) study was conducted previously and demonstrated safety and tolerability of a single i.a. injection of LNA043. This study will support the further development of LNA043 in other clinical studies, planned to include a multiple i.a. injection regimen.

## 2 Study objectives and endpoints

### 2.1 Primary objective(s)

Primary objective(s)	Endpoints related to primary objective(s)

• To assess the efficacy of a single LNA043 i.a. injection in regenerating hyaline cartilage tissue at the donor sites of patients undergoing autologous chondrocyte implantation (ACI)

	

• Cartilage glycosaminoglycan (GAG) content and bi-layer collagen organization based on 7T MRI at Week 4

• To assess safety and tolerability of a single LNA043 i.a. injection in patients undergoing ACI

	

• Adverse Events

• ECGs

• Vital signs

• Hematology, blood chemistry, urinalysis

• Physical examination

### 2.2 Secondary objective(s)

Secondary objective(s)	Endpoints related to secondary objective(s)

• To assess extent and quality of the repair tissue at the donor site before surgery

	

• International Cartilage Repair Society (ICRS) II histology scoring system at Week 4

• Percentage (%) of donor site filling based on 7T MRI at Week 4

• To assess over a longer term the extent and quality of filling of the donor site

	

• Percentage (%) of donor site filling based on 7T MRI at Week 12 and 28

• Cartilage GAG content and bi-layer collagen organization estimated using 7T MRI at Week 12 and 28

• To evaluate local and systemic pharmacokinetics (PK) of LNA043 following a single i.a. administration

	

• Serum PK profile of LNA043 and AngPTL3, Cmax and AUC

• Concentration of LNA043 and AngPTL3 in synovial fluid at Week 4

• To assess the potential immunogenicity of LNA043

	

• Presence and characterisation of anti-LNA043 antibodies in serum at Day 1 (predose), Day 8, 29, 85, 197

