At Week 4 (Day 29 -3), MRI assessment of the donor site and of the defect site has to be performed on Day 29 or up to 3 days before. Surgery can be done on the same day of the 4 Week MRI, but MRI should be performed before surgery. .

Site should plan the open ACI graft implantation at Week 4 (Day 29 +/-5). However, in case the *in vitro* culture of the ACI graft takes longer than planned, or for any other unforeseeable reason related to surgical planning or to patient's needs, the second surgery can be delayed, after informing Sponsor. On the day of the open ACI graft implantation patients will return to the hospital and safety laboratory testing will be collected.

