### Corporate Confidential Information

All MRI assessments at Day 3, Week 4, Week 12 and Week 28 (EOS) will be performed at the specific site called investigational site for medical device (subsequent in the protocol referred to as imaging site, for simplicity).

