**Corporate Confidential Information**

This may facilitate proof of concept while (i) minimizing the number of patients involved, because of the standardization of the donor sites; (ii) reducing the typically long observation time to detect cartilage tissue regeneration, because of the very small size of the donor sites; (iii)

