**Corporate Confidential Information**

Second, no additional discomfort to the patients will be created by the planned assessments, because (i) they normally undergo two surgeries according to the standard ACI protocol; (ii) MRI is a non-invasive imaging method; (iii) a biopsy of donor sites is not associated with additional morbidity ([McCarthy et al 2016](#)); (iv)

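### Does the Week 4 donor-site biopsy undermine the Week 12 and 28 MRI results because no scan follows it?

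*Protocol*

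**What the plan says.** Protocol section 2.2 sets two secondary objectives for the donor site. The first concerns repair tissue before surgery and includes "International Cartilage Repair Society (ICRS) II histology scoring system at Week 4". The second concerns the longer term: "Percentage (%) of donor site filling based on 7T MRI at Week 12 and 28", plus GAG content and collagen organization at those visits.

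Protocol section 3.2 treats a biopsy as part of the assessments and justifies it on patient burden: "they normally undergo two surgeries according to the standard ACI protocol", and "a biopsy of donor sites is not associated with additional morbidity". It also expects a short observation time "because of the very small size of the donor sites".

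Protocol section 3.1 fixes the order of events. On imaging: "All MRI assessments at Day 3, Week 4, Week 12 and Week 28 (EOS) will be performed at the specific site". At Week 4: "Surgery can be done on the same day of the 4 Week MRI, but MRI should be performed before surgery". Graft implantation is planned for Day 29 +/-5, but "the second surgery can be delayed, after informing Sponsor".

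SAP sections 6.1.1 and 6.2.1 take Day 3 as baseline for GAG, collagen and filling. SAP section 6.2.3 analyses the Week 4 ICRS score separately by biopsy type. Protocol section 8.5.1 leaves the details of image analysis to the imaging protocol.

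**The concern.** Histology and MRI are meant to describe the same repair tissue in a very small defect. If tissue is cut out after the Week 4 scan and nothing images the site until Week 12, no image shows what the biopsy left behind. A fall in filling after Week 4 could then be tissue lost to the biopsy, a true loss of repair, or both. A rise could be healing of the biopsy wound. A smaller difference between arms could be dilution and not a fading effect.

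Weeks 12 and 28 are the only longer-term efficacy visits, and protocol section 1.4 says the study will support later studies with repeated injections. Misreading a post-biopsy fall as lost effect, or a persisting difference as durability of the Week 4 tissue, could mislead that decision. The protocol defends the biopsy on morbidity only, and its section on sensitivity analyses is marked not applicable.

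**Working it through.** The plan states no figure to reproduce here. The check is the order of events, followed by arithmetic on assumed values.

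**Is the biopsy after the Week 4 MRI?** The documents do not say so in one sentence. It is inferred from three facts: the histology endpoint is at Week 4, Week 4 is the time of the second surgery, and the biopsy is justified by the two surgeries patients already have. The inference is reasonable.

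**Time from biopsy to the next scans.**
- Surgery window: Day 29 +/-5, so Day 24 to 34. The Week 4 MRI falls on Day 26 to 29 and comes first, so surgery after an in-window scan is Day 26 to 34.
- Week 12 MRI: visit Day 85 +/-5, scan +/-3, so Day 77 to 93. Interval: 77 - 34 = 43 to 93 - 26 = 67 days; nominal 85 - 29 = 56.
- Week 28 MRI: visit Day 197 +/-7, scan +/-7 (footnote 17 of the assessment schedule, taken to apply to Week 28), so Day 183 to 211. Interval: 183 - 34 = 149 to 211 - 26 = 185 days; nominal 197 - 29 = 168.
- A delayed surgery shortens these intervals. One delayed past the Week 12 scan would make that scan pre-biopsy.

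**What a biopsy could do to filling (assumed values).** Take Week 4 filling of 60% on drug and 40% on placebo, a gap of 20 points. Let the biopsy remove a share q of the repair tissue and let a share g of the remaining void regrow, equally in both arms. With x = (1 - q) x Week 4 filling, later filling = x + g(1 - x), so later gap = (1 - q)(1 - g) x Week 4 gap.

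| q | g | Drug | Placebo | Gap |
|---|---|---|---|---|
| 0 | 0 | 60 | 40 | 20 |
| 0.25 | 0 | 45 | 30 | 15 |
| 0.50 | 0 | 30 | 20 | 10 |
| 0.25 | 1/3 | 63.3 | 53.3 | 10 |
| 0 | 0.50 | 80 | 70 | 10 |

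Three things follow.
- A gap of 10 is compatible with quite different histories, one of them (q = 0) with no tissue removed at all. Regrowth alone can shrink the gap.
- The levels differ between those histories (30/20, 63.3/53.3, 80/70). With a common q and g, the two arm means would separate them. They cannot if regrowth differs by arm, because two means do not determine one q and two values of g.
- If the same volume is removed in both arms, for example 20 points, filling becomes 40 and 20 and the gap stays at 20. Levels fall and the contrast does not.

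**Which planned results are touched?** The Week 4 comparison uses a scan taken before surgery. The Week 12 and 28 changes are taken from Day 3, a valid start for cumulative filling. No visible text plans a change from Week 4 to Week 12 or 28, or says that a decline will be read as lost effect.

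**The case for a change.** The best case for changing the plan is that the remedy looks cheap: label the late results as post-biopsy, list biopsy type and days from biopsy to scan by arm, and add a supportive analysis of unsampled tissue. Biopsy type is already used, and the SAP was itself updated after database lock to separate biopsy types. With 12 planned completers in Cohort 1 at 2:1, so 8 against 4, sampling could also differ between arms by chance.

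What stands is the caution on interpretation: change after Week 4 at a sampled site does not show natural course. The rest is weaker.

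- A label and a listing alter no estimate, interval or comparison.
- Ruling in advance that a decline will not be read as loss of effect is hard to defend when the biopsy effect may be nil.
- The unsampled-tissue analysis would mean re-segmenting images after lock with readers still blinded. It also needs an unsampled site or a recorded biopsy location, and the documents show neither.
- The imbalance argument reads too much into biopsy type. The SAP gives curette scrapings a Day 1 baseline, yet the donor defect is only created on Day 1, so that specimen cannot be repair tissue. The text does not say where scrapings are taken, whether each patient gives one type or several, or whether types differ in volume. A probability of imbalance would rest on invented inputs.
- The protocol often writes of donor sites in the plural. If one is sampled and another followed, the concern falls away. The plural is not used consistently, so this stays open.

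**Conclusion.** No change to the plan is needed. The sequence is as described: a planned donor-site biopsy, apparently at the Week 4 surgery, follows the Week 4 MRI, and no scan is scheduled until Week 12. If the sampled tissue lies in the measured region and is not masked, the late filling, GAG and collagen results describe treatment followed by biopsy. They remain a valid randomised comparison from Day 3, because both arms follow the same schedule; bias would need sampling to differ by arm.

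The size cannot be fixed from the documents. In the example without regrowth, a 20-point gap stays at 20 under equal-volume removal and falls to 15 or 10 if 25% or 50% of repair tissue is lost. No figure or direction is offered for GAG or T2. This rests on the biopsy being at the second surgery and on assumed values of q and g.

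Using tissue from an already planned operation, at the price of a less clean view of later visits, is a fair trade-off in a non-confirmatory study that ended early and is past database lock. A careful author of the study report will describe the Week 12 and 28 donor-site results as post-biopsy and cite any masking in the imaging protocol. That needs no amendment.
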